#### **Step 4: Fluoroscopy**

At the conclusion of the recording, several fluoroscopic images will be taken to capture the position of the tDCS and sECoG electrodes in situ. Fluoroscopy is already used in the standard of care DBS procedure to verify placement of the DBS lead. Finally, the tDCS electrodes, sECoG electrode and VR goggles will be removed.

#### **Subject Followup**

Following removal of electrodes (and the VR goggles for awake, frameless DBS patients), the DBS procedure will then be completed. Research staff will follow up with each participant by phone within a week of the procedure to make sure the participants are not having any problems. Additionally, research staff will review each participant's medical record at 30 days after the procedure to collect information on clinical outcomes and any additional treatments, tests or procedures the participant may have had in the postoperative period.

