machines is in case the server is interrupted and it is necessary to reconstruct the data. Portions of data will be copied to end-user devices (e.g., desktop, laptop, etc) for data analysis, however only the portion needed for analysis will be copied. As with data acquisition machines, any end-user device such as a laptop that physically leaves the lab will be encrypted (while desktop machines that do not leave the lab will not be encrypted). All data on data acquisition and end-user devices will be deleted at the conclusion of the study. A linking database associating the participant ID and patient identifiers will be maintained on MUSC Box, separately from the research data. Patient identifiers to be collected include first and last name, medical record number, gender, and telephone numbers. Telephone and medical record numbers are required for the 7-day phone call and 30-day chart reviews. Findings from the phone call and chart review will be stored in the linking database. Additionally we will collect information pertaining to disease severity for each subject, including year of diagnosis, laterality of worst symptoms, laterality of surgery, and pre- and post-surgical scale ratings. These measures will assist in correlating our physiological data with severity of disease for each subject. Photography and videography data will be stored in the identifiable folder on the password protected network server as well. The purpose of this data is to correlate movement dynamics with the ECoG signal. Finally, radiographic imaging data is used to plan the DBS surgery for each patient. We will save this data on a password protected network server in order to analyze and correlate with our physiological data. Only IRB-approved personnel will have access to the linking database. Consent forms will be stored in a locked cabinet in a locked laboratory in the Clinical Sciences Building at MUSC.

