### **Safety reporting to the DSMB**

Subjects may report safety issues with the study directly to the PI, any member of the PI's clinical and/or research teams, the MUSC Family Care Liaison, the IRB and/or ORI Director. In the absence of any such reports, the PI will systematically attempt to uncover any safety issues experienced by a subject during the one week followup phone call and/or 30-day chart review. Any of the following will be reported to the DSMB if noted by the subject during the one week followup phone call: severe headache unresponsive to pain medication, repeated falls/imbalance, excessive bleeding from wounds, scalp irritation or bleeding, change in vision, seizure(s), and/or return to the hospital. Any of the following will be reported to the DSMB if noted during the 30-day chart review: return to hospital, evaluation by another provider for findings related to deep brain stimulation surgery, imaging, lab values and/or other reports indicating complications from deep brain stimulation surgery. All the above-mentioned issues are outside of what would be reasonably expected for a normal postoperative course following deep brain stimulation. In accordance with HRPP Section 4.7, all the above-mentioned issues constitute adverse events and will be submitted to the DSMB for review (at 6 month intervals) in addition to being recorded in the adverse events log. Events that are unexpected, related or possibly related to a subject's participation in the research and suggests that the research places subjects or others at greater risk of harm than was previously known or recognized constitute Unanticipated Problems Involving Risks to Subjects or Others (UPIRSOs) and must be reported directly to the IRB (in addition to the DSMB). Finally, all deaths will be reported to the IRB within 24 hours of learning of the death, unless the death is expected (e.g., due to disease progression).

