### **sECoG**

Insertion of electrodes onto the brain surface may precipitate bleeding from a ruptured blood vessel, damage to nearby structures, and increased risk of infection due to foreign body. These risks were outlined in a recent study (Panov et al, 2017) documenting 200 cases of sECoG insertion during DBS surgery in which all study related procedures took place in 20 minutes or less. In this study, 2 sECoG electrodes were unable to be inserted due to resistance and 8 others were associated with some complication, none of which were directly related to sECoG placement. The overall complication rate (again unrelated directly to sECoG insertion) was 5% (which is equivalent to the overall complication rate of DBS surgery without sECoG insertion) and **no infections related to the sECoG electrode occurred.** Nevertheless, to mitigate the risk of infection associated with sECoG placement, we will limit the total time dedicated to this study to 20 minutes. These electrodes come prepackaged sterilely and will be handled using standard operating room sterile procedure. Moreover, large cortical veins noted on preoperative imaging during surgical planning and/or any resistance detected during insertion will trigger immediate removal of the electrode, withdrawal of the patient from the study, and continuation with the DBS procedure.

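### The study schedules no participant contact after a call in the first week, so later complications treated elsewhere can go unrecorded

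*Combined protocol and SAP*

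**What the plan says.** Section 9.0 (Subject Followup) sets two follow-up steps. The first is a phone call: "Research staff will follow up with each participant by phone within a week of the procedure". Section 13.0 repeats this timing. Neither section gives an earliest day, a window or a rule for participants who cannot be reached. Section 10.0 names the contact differently: "Telephone and medical record numbers are required for the 7-day phone call and 30-day chart reviews". Section 11.0 (Safety reporting to the DSMB) calls it a one-week call.

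The second step is a record review: "research staff will review each participant's medical record at 30 days after the procedure". Section 9.0 presents it as additional to the call, so both are required for every participant.

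Section 11.0 says what each step should pick up. Subjects have an unprompted route: "Subjects may report safety issues with the study directly to the PI", or to several other named parties. Where no such report arrives, "the PI will systematically attempt to uncover any safety issues experienced by a subject during the one week followup phone call and/or 30-day chart review". For the chart review, the reportable items begin with "return to hospital, evaluation by another provider for findings related to deep brain stimulation surgery" and go on to imaging, laboratory values and other reports that indicate complications of the DBS surgery. An item counts only if it is noted in that review. The documents describe no second call and no request for records from other institutions.

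**The concern.** Section 13.0 (sECoG) says that inserting the strip "may precipitate bleeding from a ruptured blood vessel, damage to nearby structures, and increased risk of infection due to foreign body". Bleeding and infection need not be apparent at a call made in the first week. From then to day 30, the study relies on what has entered the medical record. The review is expected to find returns to hospital and visits to other providers, but the participant is not asked about them, and the documents do not say how care elsewhere would enter the record.

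These data are what the DSMB sees at its six-monthly reviews. With 25 subjects and few expected events, one unrecorded complication would noticeably change the safety summary. Whether an event was related to the strip, the stimulation or the DBS surgery can be judged only if the event is found.

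**Working it through.** **Setting the sections side by side**

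| Place in protocol | First contact | Later active step |
|---|---|---|
| 9.0, Subject Followup | phone, any day in the first week | record review at 30 days |
| 13.0, opening text | same as 9.0 | same as 9.0 |
| 10.0, Data Management | described as a 7-day call | 30-day chart review |
| 11.0, Safety reporting | described as a one-week call | 30-day chart review |

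A call on day 1 satisfies sections 9.0 and 13.0 as written, but not the natural reading of 10.0 or 11.0. All four places agree that no scheduled participant contact follows the call.

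**Which events can escape.** To be missed, a complication must (a) appear after the call, (b) be absent from the record reviewed at 30 days, and (c) not be reported by the subject unprompted. Care received elsewhere is the obvious way to meet (b).

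**Illustration of size.** The plan has no figure of its own to reproduce. Inputs:
- n = 25 subjects (section 5.0).
- p = 2% to 5%, the rate of surgery-related complications of DBS (section 1.0). Section 13.0 also gives 5% overall in the 200-case series.
- f = 10% to 30%, the share of complications that meet all of (a) to (c). **This is an assumption; the documents give no value.**

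Expected number of subjects with a complication = n × p: 25 × 0.02 = 0.5 and 25 × 0.05 = 1.25.

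Chance of at least one complication = 1 − (1 − p)^25: 39.7% at 2% and 72.3% at 5%.

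Chance of at least one missed event = 1 − (1 − p × f)^25, treating subjects as independent:

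| p | f = 10% | f = 30% |
|---|---|---|
| 2% | 1 − 0.998^25 = 5% | 1 − 0.994^25 = 14% |
| 5% | 1 − 0.995^25 = 12% | 1 − 0.985^25 = 31% |

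**Limit on what p means.** Section 13.0 says that the complications in the 200-case series were not directly related to the strip. The 5% may also include the 2 failed insertions: (2 + 8)/200 = 5%, against 8/200 = 4% without them. A failed insertion is seen in the operating room and cannot be missed later. The table therefore illustrates complications of any cause.

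**The case against.** The strongest reply is that ascertainment is better than it first looks, and that little depends on it.

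- **Call timing.** Sections 10.0 and 11.0 point to a call at about one week, and some items on its list, such as repeated falls or a return to hospital, suggest a patient who has already gone home. This stands: a day-1 call is permitted by the wording of two sections but is not the likely intention. The timing conflict alone is a matter of wording.
- **Whether one contact could replace the other.** A reader might infer from the phrase "during the one week followup phone call and/or 30-day chart review" that either contact may be skipped. The documents do not support that. Section 9.0 requires both for each participant, and section 11.0 gives a separate reporting list for each. The phrase describes where an issue may come to light.
- **Whether anyone asks later.** A reader might infer that nobody asks the participant anything after the first week. That is not established. Section 10.0 collects post-surgical scale ratings at an unstated time, the investigator is also the surgeon (section 7.0), and subjects may report problems by several routes. What stands is narrower: the study schedules no active contact after the call.
- **Care elsewhere.** The chart review explicitly looks for evaluation by other providers and is not limited to events at this institution. That helps when such care is recorded, but the documents provide no step to make sure that it is.
- **Consequence.** Both aims are electrophysiological, no safety rate is an endpoint, and the stopping rule is qualitative. Even with complete ascertainment, 0 events in 25 leaves a one-sided 95% upper bound of 1 − 0.05^(1/25) = 11.3%. A second call would not make the study informative about rare harm. This limits how much weight the point can bear, but the DSMB's judgement still depends on the events it is shown.

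**Conclusion.** The point holds in a limited form. After one call in the first week, the study actively seeks events only in the medical record, so a later complication treated elsewhere can be missed unless it reaches that record or the subject volunteers it. The documents do not show that events will be missed, and they do not allow the loss to be computed.

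The range of 5-14% (2% rate) to 12-31% (5% rate) rests on an assumed 10-30% escaping, on independence between subjects and on follow-up of all 25. It should not be read as the risk of missing a strip complication: the underlying rates concern DBS complications overall, and the 200-case series reported no strip-related infections.

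This is an inexpensive improvement to safety ascertainment. It does not affect the validity of the electrophysiological analyses.

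**What to change.** 1. In section 9.0 and section 11.0, add a phone call to each participant when the 30-day chart review is done. Use the safety questions already listed in section 11.0 for the first call, and add one on any care received from another hospital or provider since surgery.
2. State one timing for the first call and use it in sections 9.0, 10.0, 11.0 and 13.0.

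The cost is at most 25 short calls by staff who already make the first call, using telephone numbers that section 10.0 already collects, plus the change of wording. The second item alone would tidy the text but would not close the gap; the 30-day call is the substantive change.

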### **10.0 Data Management**

Once a patient is screened, they will be assigned a participant ID. Participant IDs will be assigned consecutively. We will maintain a database that accurately reflects all the patients that were screened and the results of eligibility evaluation (screen failure vs enrolled). For enrolled subjects, the specific types of data that will be collected include: 1) analog local field potentials from the sECoG electrode, 2) digital and analog output signals from the tDCS and VR goggle devices, 3) photography and videography data, and 4) imaging data (dicom files). Raw data will remain on data acquisition machines with encrypted hard drives and stored behind a locked door when not directly supervised in the operating room. Data will be copied from all data acquisition machines to a password protected network server under the participant ID. This will constitute the master copy of all data for the lab and will consist of separately stored coded and identifiable folders. The purpose of keeping a copy of the raw data on the data acquisition

machines is in case the server is interrupted and it is necessary to reconstruct the data. Portions of data will be copied to end-user devices (e.g., desktop, laptop, etc) for data analysis, however only the portion needed for analysis will be copied. As with data acquisition machines, any end-user device such as a laptop that physically leaves the lab will be encrypted (while desktop machines that do not leave the lab will not be encrypted). All data on data acquisition and end-user devices will be deleted at the conclusion of the study. A linking database associating the participant ID and patient identifiers will be maintained on MUSC Box, separately from the research data. Patient identifiers to be collected include first and last name, medical record number, gender, and telephone numbers. Telephone and medical record numbers are required for the 7-day phone call and 30-day chart reviews. Findings from the phone call and chart review will be stored in the linking database. Additionally we will collect information pertaining to disease severity for each subject, including year of diagnosis, laterality of worst symptoms, laterality of surgery, and pre- and post-surgical scale ratings. These measures will assist in correlating our physiological data with severity of disease for each subject. Photography and videography data will be stored in the identifiable folder on the password protected network server as well. The purpose of this data is to correlate movement dynamics with the ECoG signal. Finally, radiographic imaging data is used to plan the DBS surgery for each patient. We will save this data on a password protected network server in order to analyze and correlate with our physiological data. Only IRB-approved personnel will have access to the linking database. Consent forms will be stored in a locked cabinet in a locked laboratory in the Clinical Sciences Building at MUSC.

## **11.0 Provisions to Monitor the Data to Ensure the Safety of Subjects**

### **Data and Safety Monitoring Plan**

The proposed research involves use of a neural stimulation device and warrants oversight by a Data Safety Monitoring Board (DSMB). The primary purpose of the DSMB is to ensure the safety of participants and the validity and integrity of data collected during the study. The overall framework involves biannual review of the enrollment, safety and adverse event data, and quality control data by the DSMB throughout the period of the proposed research.

### **DSMB composition**

The DSMB will be appointed by the PI and will be composed of individuals who are not on the study team and have the following qualifications: (1) a board-certified Movement Disorders neurologist who also is a movement disorders researcher and is experienced in care of movement disorders patients, (2) a biostatistician with expertise in design and analysis of clinical trials and (3) a clinical electrophysiologist with expertise in transcranial stimulation and intraoperative monitoring. These three individuals bring substantial expertise adequate to monitor data and safety for the proposed research.

### **DSMB responsibilities**

The responsibilities of the DSMB are as follows. Prior to any enrollment, the DSMB will review the study design, protocol, recruitment/enrollment plan, statistical analysis plan, and data and safety monitoring plan. Once enrollment begins, the DSMB will convene every 6 months to review the enrollment data, the safety and adverse event data and quality control data (see below for detailed data description). The DSMB will review the aggregated summary data as well as the individual participants' data (de-identified). The DSMB may provide

recommendations for any safety concerns. The DSMB may recommend stopping the study early if the protocol has significant safety concerns. The DSMB will review the results and document their reviews in writing. In summary, the stopping rules are if the study has unanticipated safety concerns. The DSMB will also be able to make recommendations for appropriate action to maintain a reasonable safety profile for the study. The PI will provide a report for the IRB to review that summarizes oversight activities, DSMB recommendations and any concerns regarding participant safety.

### **Safety reporting to the DSMB**

Subjects may report safety issues with the study directly to the PI, any member of the PI's clinical and/or research teams, the MUSC Family Care Liaison, the IRB and/or ORI Director. In the absence of any such reports, the PI will systematically attempt to uncover any safety issues experienced by a subject during the one week followup phone call and/or 30-day chart review. Any of the following will be reported to the DSMB if noted by the subject during the one week followup phone call: severe headache unresponsive to pain medication, repeated falls/imbalance, excessive bleeding from wounds, scalp irritation or bleeding, change in vision, seizure(s), and/or return to the hospital. Any of the following will be reported to the DSMB if noted during the 30-day chart review: return to hospital, evaluation by another provider for findings related to deep brain stimulation surgery, imaging, lab values and/or other reports indicating complications from deep brain stimulation surgery. All the above-mentioned issues are outside of what would be reasonably expected for a normal postoperative course following deep brain stimulation. In accordance with HRPP Section 4.7, all the above-mentioned issues constitute adverse events and will be submitted to the DSMB for review (at 6 month intervals) in addition to being recorded in the adverse events log. Events that are unexpected, related or possibly related to a subject's participation in the research and suggests that the research places subjects or others at greater risk of harm than was previously known or recognized constitute Unanticipated Problems Involving Risks to Subjects or Others (UPIRSOs) and must be reported directly to the IRB (in addition to the DSMB). Finally, all deaths will be reported to the IRB within 24 hours of learning of the death, unless the death is expected (e.g., due to disease progression).

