### **Exclusion criteria:**

- Patients unable to actively participate in the consent process physically and/or cognitively

- Presence of scalp injury or disease
- Prior intracranial surgery with the exception of deep brain stimulation surgery
- Prior brain radiotherapy
- Prior history of intracranial tumor, intracranial infection or cerebrovascular malformation
- Prior history of seizures

The rationale for these criteria are as follows: The major risks to subjects in this study consist of #1) scalp irritation from the tDCS electrodes and #2) damage to the cortical surface or surrounding structures (such as cortical bridging veins) during insertion of the sECoG electrode. The subdural space between the skull and cortical surface can be compromised by scarring from intracranial surgery (at the site of sECoG insertion), brain radiation and/or infection of the brain. Furthermore, abnormalities of cortical vasculature, such as with an intracranial tumor or cerebrovascular malformation, may impede safe insertion of the sECoG electrode. Finally, history of seizure disorder may indicate underlying cortical abnormalities that might confound our data analysis.

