### **tDCS**

Commonly reported side effects of tDCS occur at the site where the electrodes are placed: local scalp itching (30.4%), tingling or burning sensations (70.6%), transient headaches or stimulation-induced skin lesions (11.8%) and contact dermatitis (1.5%). Report of headache or scalp lesion on visual inspection during the stimulation will trigger immediate removal of the electrodes, withdrawal of the patient from the study, and continuation with the DBS procedure. Furthermore, the electrodes will be sterilized with ethylene oxide prior to the procedure and will be secured in place with iodine-impregnated adhesive film, which will serve as an additional measure against any possible infection.

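### The 30-day DSMB triggers, apart from return to hospital, are tied to DBS surgery, so a complication attributed to tDCS or sECoG and first charted after the one-week call meets no stated trigger

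*Combined protocol and SAP*

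**What the plan says.** Section 11.0 (Safety reporting to the DSMB) gives two lists of reportable findings, one for each follow-up contact.

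- **One-week phone call**, if noted by the subject: "severe headache unresponsive to pain medication, repeated falls/imbalance, excessive bleeding from wounds, scalp irritation or bleeding, change in vision, seizure(s), and/or return to the hospital".
- **30-day chart review**: return to hospital, and "evaluation by another provider for findings related to deep brain stimulation surgery, imaging, lab values and/or other reports indicating complications from deep brain stimulation surgery".

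The same section then makes these lists the working definition: "all the above-mentioned issues constitute adverse events and will be submitted to the DSMB for review (at 6 month intervals", and they are also entered in the adverse events log. A separate route to the IRB and the DSMB exists for unanticipated problems (UPIRSOs).

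The research risks are stated elsewhere. The rationale in section 4.0 gives the major ones as "1) scalp irritation from the tDCS electrodes and #2) damage to the cortical surface or surrounding structures". Section 13.0 (tDCS) adds skin lesions and contact dermatitis. Section 13.0 (sECoG) says that insertion "may precipitate bleeding from a ruptured blood vessel, damage to nearby structures, and increased risk of infection due to foreign body".

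**The concern.** The Data and Safety Monitoring Plan in section 11.0 justifies having a DSMB by the use of a neural stimulation device. Yet the 30-day list, the last scheduled look at each participant, mentions neither that device nor the recording electrode. Apart from readmission, an event qualifies there only if it is linked to the clinical operation.

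Whether an event is reportable then depends on when it is first noted and what it is attributed to. Scalp irritation mentioned on the call is reportable. The same finding charted a week later by the surgeon, and put down to the tDCS electrodes, is not. The board's six-monthly reviews and its advice on stopping rest on this feed, so the count it sees would depend partly on wording. The data are not lacking: section 9.0 (Subject Followup) has staff gather outcomes and further care from the record at 30 days. The reporting rule narrows what is passed on.

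**Working it through.** The plan states no figure on this point, so the check sets the lists beside the stated risks.

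**Overlap.** The call list has 7 items. The 30-day list has 3: return to hospital; evaluation by another provider for DBS-related findings; and imaging, laboratory or other reports indicating DBS complications. Only return to hospital is on both.

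| Research risk | Named in | One-week call list | 30-day list |
|---|---|---|---|
| tDCS-site irritation, lesion, dermatitis | 4.0, 13.0 (tDCS) | Covered if it counts as scalp irritation or bleeding | Not named; only through readmission or attribution to DBS surgery |
| Bleeding | 13.0 (sECoG) | Wound bleeding, severe headache | Same condition |
| Damage to cortex or nearby structures | 4.0, 13.0 (sECoG) | Partly: vision, seizure, falls/imbalance; not weakness, speech or cognition | Same condition |
| Infection | 13.0 (sECoG) | No sign named | Same condition |

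**Tracing the tDCS case.** Suppose a lesion is first charted after the call, at a visit to the operating surgeon.

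1. Call list: not met, because the call has passed.
2. Return to hospital: not met if an outpatient visit does not count as one (my reading).
3. Evaluation by another provider: not met. Section 7.0 says that the PI is the surgeon, and in any case the evaluation must be for DBS-related findings.
4. Reports indicating DBS complications: not met if the lesion is attributed to tDCS. The protocol itself separates such attributions: section 13.0 (sECoG) reports complications in a published series while stating that none arose directly from sECoG placement.
5. UPIRSO route: it requires an unexpected event that suggests more risk than was known. Skin lesions and dermatitis are already listed risks, so they would ordinarily not qualify.

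**Tracing the call case.** Suppose a subject reports wound drainage or new weakness on the call, it is never charted and there is no readmission. It is not on the call list. Under section 10.0, call findings go to the linking database, whereas the 30-day step reads the medical record, so the event need not reappear.

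**Scale only.** With 25 enrolled (section 5.0) and the rates in section 13.0 (tDCS):

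- headache or skin lesion, 11.8%: 25 × 0.118 = 2.95 expected; chance of at least one = 1 − 0.882^25 = 0.957;
- contact dermatitis, 1.5%: 25 × 0.015 = 0.375 expected; chance of at least one = 1 − 0.985^25 = 0.315.

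These are events at any time. The first rate pools headache with skin lesions. The share first charted after the call is not given, so neither figure is a number of missed events.

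**The case against.** The strongest reply is that little would slip through.

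- **The lists are not stated to be exclusive.** Section 11.0 also has the PI look for safety issues of any kind, lets subjects report directly, and has the DSMB review safety data in aggregate and by participant. This is fair, but the first two provisions concern detection. No sentence sends an unlisted event that is not a UPIRSO to the board.
- **The lists serve different sources.** One covers symptoms told by phone, the other documents in a chart. Different wording is reasonable, and the mismatch alone is not a defect. It does not explain why the chart list leaves out the research procedures.
- **Infection and deficit are mostly caught.** The sECoG strip goes through the DBS burr hole (section 3.0, Procedure steps), so a charted infection or deficit would ordinarily be recorded as a surgical complication and qualify at 30 days. This stands, and it confines the call-list gap to events that are never charted.
- **The tDCS case needs several misses.** Research time is limited to 20 minutes, a lesion seen during stimulation leads to withdrawal, and scalp irritation is a call item. A missed lesion must be absent or unnoticed at both points and then cause no readmission. This stands, and it limits the likely number.

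**Conclusion.** The point holds in a limited form. As written, the 30-day rule omits the study's own intervention. A complication attributed to tDCS or sECoG, charted after the call and without readmission, has no stated path to the DSMB unless it is a UPIRSO. The gap at the call is smaller. This is an inexpensive improvement to a reporting rule; it affects no sample size, power or error rate.

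The conclusion assumes that the lists are applied literally, that participants see the surgeon between the call and day 30 (the protocol does not describe such visits), and that another provider means someone other than the surgeon.

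A reader might infer more than the documents support:

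- **That neither list reflects the research risks.** The call list names scalp irritation, bleeding, vision change, seizure and falls/imbalance. It is incomplete, not unrelated.
- **That infections and neurological deficits generally go uncounted.** Once charted, they would ordinarily qualify at 30 days as surgical complications.
- **That about 3 events would be missed.** The 2.95 above pools headache with skin lesions and is not restricted to late-charted events.
- **That a loss of infection reports can be calculated.** It would need an infection rate and a capture fraction, and the documents give neither. The 5% in section 13.0 (sECoG) is an overall complication rate, from a series of 200 cases with no sECoG-related infection.

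**What to change.** In section 11.0 (Safety reporting to the DSMB):

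1. Keep both lists, including the imaging, laboratory and other-provider triggers. One merged list built from the call items could drop these.
2. In the 30-day list, wherever the wording refers to DBS surgery, make it DBS surgery or the research procedures (tDCS, sECoG), whoever evaluates the patient.
3. Carry the scalp item from the call list into the 30-day list, and state that it includes lesion or dermatitis at a tDCS site.
4. Add signs of wound or intracranial infection and new neurological deficit to the call list.
5. Record relatedness (DBS surgery, tDCS, sECoG) as a separate field in the adverse events log, so that attribution describes an event and does not decide whether it is reported.

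The cost is a wording change, a few more questions on an existing call and one log field. The 30-day record review already takes place. The small downside is a few more minor scalp events in the DSMB report.
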